1. INTRODUCTION

1.1 SUMMARY

Pain is a common co-morbidity for HIV-infected patients. Prevalence studies suggest that, on average, half of all HIV-infected persons suffer pain. Chronic pain can lead to heavy alcohol use among HIV-infected persons, which may in turn be a barrier to treatment/control of HIV and contribute to spread of HIV. Thus there is an urgent need to address pain among persons with HIV. Opioid receptor antagonists such as naltrexone and nalmefene, which are licensed for treatment of alcohol use disorders, show promise as being effective and safe treatments for chronic pain among persons with HIV. The specific aim of the research is to assess the feasibility, tolerability and safety of using opioid receptor antagonists (low-dose naltrexone and standard-dose nalmefene) to treat pain among HIV-infected persons with heavy alcohol use and chronic pain. If milestones are met, the next phase of the study - UH3, will aim to perform a 3-arm pilot randomized, double-blinded, placebo-controlled study of low-dose naltrexone and standard-dose nalmefene vs. placebo among HIV-infected persons with heavy alcohol use and chronic pain to provide estimates of their effects on: 1) pain (both self-reported and experimental/cold pressor test; 2) inflammation (i.e., levels of inflammatory cytokines IL-6 and TNF- α); and 3) measures of HIV control (CD4 count and viral load). We choose to conduct this research in St. Petersburg, Russia, given that: 1) nalmefene is licensed in Russia, but not currently in the US; 2) patients are seldom on chronic opioids (which are contraindicated to use with opioid receptor antagonists) due to the unavailability of opioid agonist therapy for addiction and restricted use of opioids for pain; and 3) a high prevalence of heavy drinking and HIV exists in Russia. Given the US epidemic of opioid use disorders, new pharmacotherapies without addictive potential are desperately needed for HIV-infected persons with chronic pain and alcohol problems.

2. OVERVIEW OF STUDY DESIGN

2.1 STUDY AIMS

Our Specific Aim will compare effects of low-dose naltrexone and standard-dose nalmefene among persons with HIV who have chronic pain:

UH2/Aim 1: To assess the feasibility, tolerability, and safety of using opioid receptor antagonists (naltrexone and nalmefene) to treat pain among HIV-infected persons with heavy alcohol use and chronic pain.

2.2 STUDY OUTCOMES

Primary Outcomes: The primary outcome for this study is tolerability of medication during treatment. Based on measurements used by other researchers, medication tolerability will be measured via a 0-100 visual analog scale with 0 anchored as “cannot tolerate at all” and 100 as “tolerate perfectly well.” Participants will be asked to estimated tolerability over the previous 2 weeks at each study visit: the primary outcome will be tolerability score at the week 8 visit.

Secondary Outcomes:

- 1) Alcohol reduction measured as a reduction in mean number of grams of pure ethanol consumed per day.
- 2) Treatment discontinuation: defined as patient self-report of stopping medication anytime during the treatment period. Participants will be instructed to notify the study staff in real-time if they discontinue medications, and they will be queried about discontinuation at the week 4 and 8 study visit assessments. Lost-to-follow-up will be assumed to be equivalent to treatment discontinuation.
- 3) Adherence: defined as self-report of the percentage of study medications taken in the past 2 weeks, using a visual analog scale (VAS) from 0 to 100, same as used to assess adherence to HIV medication. Participants will be asked to mark on the ruler what percentage of medication they have taken that week ("0% means no medication, 50% means half your medication, 100% means all your medication"). In addition, medication adherence will be assessed by Riboflavin (50 mg) that will be included in the capsules by the pharmaceutical laboratory. This allows for assessment of medication adherence in both medication arms. Visual inspection of the urine for the presence or absence of riboflavin using ultraviolet (UV) light at the long wave setting (33 nm) in a room with low ambient light will be conducted.
- 4) Reported side effects. We will use a Symptom Checklist based on side effects reported in prior studies of naltrexone, plus an open-ended question to assess for any side effects from study medications in the past 4 weeks at visits 4 and 8. Participants side effects will be rated by trained research assessors, using the Guidelines for Severity Grades (mild, moderate, severe, and life-threatening, death) (See Box 1).
- 5) Medication Satisfaction: This 14-item questionnaire assesses satisfaction with medication to treat chronic conditions and difficulty/inconvenience of use.
- 6) Severe hepatotoxicity: we will test aminotransferase levels (AST/ALT) at baseline and at 4 and 8 weeks to look for severe hepatotoxicity defined as $AST/ALT > 10X$ the level of normal. Hepatotoxicity rarely occurs in the setting of treatment with naltrexone among persons with HIV;¹ less is known of the safety of nalmefene among persons with HIV, however hepatotoxicity is not listed as an adverse event in the product insert. This threshold was selected as it is 10X upper limit of normal (ULN) recognizing that the population with alcohol use and commonly hepatitis C may start off with AST and ALT above the ULN. Any elevation in AST/ALT beyond ULN will be evaluated by the investigators as a potential adverse event: if elevations are felt to be dangerous/life-threatening medications may be stopped at an even lower threshold. We consulted with experts in the field, with one (Yale Professor of Medicine, NIDA researcher who has done research involving Naltrexone) noting that "Grade 4 (10x) is the standard for STOPPING and monitoring for all of these trials UNLESS there is a clear indication that toxicity is a major concern (which it is not here based on a large amount of literature)."² (Springer et al., 2012)

[figure not shown]
For feasibility, descriptive purposes, and to refine our measurements, we will also assess pain (self-reported and experimental) at baseline, week 4 and week 8.

2.3 STUDY DESIGN

This is a randomized, double-blinded, 2-arm study of 16 participants with HIV, chronic pain (defined as any bodily pain of moderate to severe intensity lasting for ≥ 3 months), and past-year heavy alcohol use, defined by NIAAA criteria. The 16 participants will be randomly assigned to either naltrexone or nalmefene with a 1:1 allocation ratio using permuted blocks to ensure equal numbers in each arm. Although we will not be formally testing differences between the naltrexone and nalmefene groups, participants will be randomized to the 2 arms in order to minimize selection bias and confounding in the allocation of interventions. Participants will be treated for 8 weeks, and outcomes (tolerability, alcohol use, side effects, medication adherence and discontinuation, and willingness/desire to continue to take medication at the end of study) will be evaluated at the end of treatment. In addition, we will review changes in pain during treatment with naltrexone and nalmefene to ensure that pain does not get worse and determine whether there is some improvement.

The study design and schedule for study visits and assessments is depicted in Figure 1. After consent and enrollment participants will be randomly assigned to either low-dose naltrexone or standard-dose nalmefene. The schedule of study in-person visits/assessments are as follows: screening visit, baseline, 2, 4, 6, and 8 weeks. At baseline, weeks 4 and 8, full study visits will occur, including assessments of tolerability of medication, medication discontinuation, treatment side effects, self-reported adherence and confirmation of adherence through riboflavin urine testing, self-reported pain, and experimental cold pain tolerance (cold-pressor test). Participants will also be instructed to keep a daily dairy to record pain severity, medication adherence, and alcohol use. Weeks 2 and 6 will be short visits at which time a brief assessment of tolerability, side effects, and adherence will occur. Throughout the course of the study, participants will be expected to come in for three in-person assessments and blood draw visits (screening/baseline, 4- and 8-weeks) and two shorter in-person visits.

Figure 1: Study Design (UH2 Phase)

2.4 STUDY SITE

Recruitment, enrollment, and all study visits will take place at the Laboratory of Clinical Pharmacology of Addictions at the First St. Petersburg Pavlov State Medical University (PSMU) in St. Petersburg, Russia. PSMU is the major educational, scientific, and clinical medical institution for northwestern Russia. Blood specimens will be processed and analyzed at ImmunoBioService (IBS).

2.5 INCLUSION CRITERIA

To be eligible to participate in the trial, participants will need to meet the following inclusion criteria:

1. 18 years or older
2. HIV-positive
3. Chronic pain (present ≥ 3 mo) of moderate to severe intensity
4. Heavy drinking past year (Based on NIAAA criteria: > 14 standard drinks per week/ > 4 drinks in a day for men; > 7 drinks in the past week/ > 3 drinks in a day for women.³³)
5. If female, negative pregnancy test and willing to use adequate birth control
6. Provision of contact information for 2 contacts to assist with follow-up
7. Address within 100 kilometers of St. Petersburg
8. Possession of a telephone (home or cell)
9. Able and willing to comply with all study protocols and procedures

2.6 EXCLUSION CRITERIA AT STUDY ENTRY

1. Not fluent in Russian
2. Cognitive impairment resulting in inability to provide informed consent based on research assessor (RA) assessment
3. Known active TB or current febrile illness
4. Breastfeeding
5. Known uncontrolled psychiatric illness (such as active psychosis)
6. History of hypersensitivity to naltrexone, nalmefene, or naloxone
7. Current use (past week) of illicit or prescribed opiates as documented by either self-report or positive urine drug test
8. Unwilling to abstain from opiates during the treatment period
9. Current use of neuroleptics
10. History of seizure disorder
11. Known liver failure
12. ALT/AST levels >5x normal
13. History of Raynaud's disease
14. Planned surgeries in the next 3 months
15. Enrolled in another HIV and/or substance use medication intervention study
16. Taking naltrexone in the past 30 days
17. Taking nalmefene in the past 30 days

2.7 RECRUITMENT GOALS

We aim to randomize 16 participants into the trial and a total of up to 30 may be enrolled, but not randomized due to not meeting study entry criteria. Existing Russia ARCH (H-31200) participants will be offered to be screened for PETER PAIN. We will also screen St PETER (H-35288) participants at their final St PETER study visit for eligibility. Recruitment beyond PSMU will occur at local NGOs and Russia ARCH network hospitals including the major clinical HIV hospitals (Botkin Infectious Disease Hospital, Leningrad Regional AIDS Center, St. Petersburg City AIDS Center) and addiction hospitals (Leningrad Regional Center for Addictions, St. Petersburg City Addiction Hospital).

2.7.A. SAMPLE SIZE CALCULATION AND POWER

The goal of this study is to assess the feasibility, tolerability and safety of low-dose naltrexone and standard-dose nalmefene to inform a larger pilot RCT. The study will not be powered to detect statistically significant differences in outcomes and formal statistical testing will not be conducted. If we detect substantial intolerance to medication (mean tolerability rated < 80), and/or if other results qualitatively suggest intolerance (i.e. we have a larger than expected percentage who report discontinuation, non-adherence, side effects, and that they would not want to continue meds), we will not proceed to the next phase (UH3). To illustrate the limits of this phase of study, we provide the width of the CIs for the tolerability outcome within each treatment group. We expect < 15% loss to follow-up at 8 weeks and assume 7 evaluable subjects in each arm. Younger et al. observed a standard deviation of 15.1 for tolerability score. Assuming a similar standard deviation for each arm of this study, the length of a 95% confidence interval for mean tolerability would be approximately 22.4 (e.g., if mean tolerability were 80, the 95% CI would span from 68.8 to 91.2) for either arm.

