3.3 INTERVENTION

As of September 18th, 2018, enrollment into arm A of the study was discontinued due to concerns about tolerability of the medication. Enrollment into arm B of the study will continue until we reach the target sample size for this arm (N=8).

Eligible participants will be randomly assigned into one of two study arms: 1) 4.5 mg naltrexone or 2) 18mg nalmefene. Study medication will be provided by trained physicians, who will instruct participants in proper medication administration and adherence.

Drug capsules containing naltrexone hydrochloride (4.5mg) and nalmefene hydrochloride dihydrate (18mg) will be prepared by NonStopPharma, a compounding pharmacy in St. Petersburg, Russia. Doses will look identical; participants and providers will be blinded to assigned medication. Both medication capsules will include Riboflavin. Participants will be instructed to take one capsule orally once per day for 8 weeks. Participants will be given 28 days' worth of medications, with instructions to bring pill bottles/leftover medications to the following visit. Although medication visits will occur every two weeks, providing participants with 28 days of medications will ensure that they will not run out even if they miss the 2 and 6 week visits.

The Food and Drug Administration (FDA) has indicated that an Investigational New Drug (IND) is not needed for studies conducted outside the United States.

3.3.A. NALTREXONE

Participants randomized to this group will receive low-dose naltrexone for 8 weeks.

Participants will be instructed to take the medication once daily for 8 weeks. Naltrexone dosing will start on the day of the baseline visit, after successful passing of the naloxone challenge. If the participant does not pass the naloxone challenge, they will be brought back within a week to try again.

The most common side effects (reported in more than 1 in 10 people) of naltrexone are difficulty sleeping, anxiety, nervousness, abdominal pain/cramps, nausea and/or vomiting, low energy, joint and muscle pain, and headache.

Uncommon side effects (reported in less than 1 in 10 people, but more than 1 in 100 people) of naltrexone are loss of appetite, diarrhea, constipation, increased thirst, increased energy, feeling down, irritability, dizziness, skin rash, delayed ejaculation, decreased potency, and chills.

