8.1 PRIMARY ANALYSES

Descriptive statistics and graphic displays of all outcome measures will be generated.

The main focus of this aim is the evaluation of tolerability within each treatment group (naltrexone and nalmefene), thus the analysis set will be all participants who receive at least one dose of their assigned intervention. We will report descriptives such as mean tolerability score at 8 weeks within each treatment group along with 95% confidence intervals (CIs). No formal testing will be conducted in this aim. If the data are skewed, transformations will be performed (e.g., log transformation) or the median will be reported if no appropriate transformation is identified. We anticipate that mean tolerability

scores at 8 weeks will not be lower than 80 (this is based on prior study of low-dose naltrexone which reported tolerability scores of 89 in both intervention and placebo). We will also evaluate: 1) mean number of grams of pure ethanol consumed per day, 2) the percentage in each group that discontinue medication during the 8 week treatment period, 3) the mean % adherence to medications in each group, 4) the percentage of participants who report severe or life threatening side effects, or experience hepatotoxicity during treatment and 5) the percentage who say that they would continue the medication if given the option. Corresponding 95% confidence intervals will be reported for each of the above variables. For binary variables, 95% exact binomial confidence intervals (CIs) will be reported.

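### The illustrated 95% CI length of 22.4 at n = 7 treats the SD as known; a t interval is 27.9 long, and the figure may no longer describe arm A

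*Combined protocol and SAP*

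**What the plan says.** Section 2.7.A (Sample size calculation and power) disclaims power and formal testing and offers a precision figure instead: "To illustrate the limits of this phase of study, we provide the width of the CIs" for the tolerability outcome in each group. Its inputs are a cited earlier study that "observed a standard deviation of 15.1 for tolerability score", a similar SD assumed in each arm, and loss to follow-up below 15%, from which the authors "assume 7 evaluable subjects in each arm". The result is that "the length of a 95% confidence interval for mean tolerability would be approximately 22.4", with the example that "if mean tolerability were 80, the 95% CI would span from 68.8 to 91.2". The statement is made for both arms. The multiplier is not named.

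Section 8.1 (Primary analyses) plans the mean week-8 tolerability score with a 95% CI within each group. It specifies exact binomial intervals for binary variables but names no method for intervals on means.

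Section 3.3 (Intervention) states that, as of 18 September 2018, "enrollment into arm A of the study was discontinued due to concerns about tolerability of the medication". Arm B continues to its target of 8. The number enrolled in arm A is not given.

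**The concern.** With 7 observations, the choice between a normal and a t multiplier is not a refinement. The SD of 15.1 is borrowed from another study for planning. The interval that section 8.1 will report has to use an SD estimated from the arm's own scores, and the extra uncertainty on 6 df is substantial. A planning width based on 1.96 will therefore be shorter than the interval the reader should expect.

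The sentence exists to show how little 7 people per arm can establish, and it errs in the direction that hides this. It also sits beside the rule not to proceed to UH3 if mean tolerability is below 80, and its example is centred on 80, so a reader will naturally use it to judge how firm such a mean is.

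Separately, the sentence assumes 7 evaluable participants in both arms, although one arm has stopped enrolling.

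**Working it through.** **Inputs.** SD 15.1, 7 evaluable per arm, 95% two-sided, illustrative mean 80 (all section 2.7.A). Sixteen participants randomized 1:1 gives 8 per arm (section 2.3), and 8 × 0.85 = 6.8, consistent with 7.

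**Standard error.** 15.1/√7 = 5.707.

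**Reproducing the plan's figure.** 2 × 1.96 × 5.707 = 22.37; limits 80 ± 11.19 = 68.8 to 91.2. This matches the plan exactly. The alternatives tried do not: t(6) at 95% gives 27.93, t(6) at 90% gives 22.18, z at 90% gives 18.78, and n = 8 gives 20.93 (z) or 25.25 (t). The plan therefore used 1.96, the known-SD formula.

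**With the SD estimated from the 7 scores.** t(0.975, 6) = 2.447.

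- Length = 2 × 2.447 × 5.707 = 27.93; limits 80 ± 13.97 = 66.0 to 94.0.
- Ratio to the plan: 27.93/22.37 = 1.248, so 25% longer. Equivalently, 1 − 22.37/27.93 = 0.199, so the stated length is 20% too short.

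**If 15.1 is the true SD rather than the sample SD.** Under normality the sample SD averages c4(7) × 15.1, with c4(7) = √(2/6) × Γ(3.5)/Γ(3) = 0.9594. The expected t length is 27.93 × 0.9594 = 26.80, and 26.80/22.37 = 1.198, about 20% longer than stated.

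**Other arm sizes at sample SD 15.1.** Section 3.3 gives no number for arm A, so the rows for 4, 5 and 6 are assumptions. The row for 8 is arm B with nobody lost.

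| Evaluable n | t multiplier | z length | t length |
|---|---|---|---|
| 4 | 3.182 | 29.6 | 48.1 |
| 5 | 2.776 | 26.5 | 37.5 |
| 6 | 2.571 | 24.2 | 31.7 |
| 7 | 2.447 | 22.4 | 27.9 |
| 8 | 2.365 | 20.9 | 25.2 |

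At n = 8 the t interval around 80 is 67.4 to 92.6.

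**If 1.96 were also used in the analysis.** The documents do not say that it would be. With n = 7 and normal scores, coverage would be P(|t6| ≤ 1.96) = 0.902, so a nominal 95% interval would cover about 90%.

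**The case against.** The strongest reply is that nothing was miscalculated. The plan takes an external SD as a planning input, labels the length approximate and the interval an example, and applies a recognised known-SD formula correctly. It plans no test, does not derive the sample size from the width, and applies its threshold of 80 to the mean itself. Either interval extends more than 10 points on each side of 80, so the message that this phase is imprecise survives. All of this is fair, and it limits the weight of the point. It does not rescue the figure: calling it approximate covers rounding, not a gap of 20 to 25%, and the known-SD formula does not describe the interval the trial can report.

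Four narrower objections also deserve an answer.

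- **27.9 presumes a sample SD of exactly 15.1.** True; 26.8 is the expected length if 15.1 is the population value. Both are well above 22.4.
- **The t interval leans on normality, on a scale capped at 100.** Section 8.1 cites earlier mean scores of 89; at that mean the t interval would run to about 103, and the z interval to about 100.2. Section 8.1 already allows transformation or the median for skewed data, so naming t cannot cover every case. This does not favour 1.96.
- **The coverage loss is hypothetical.** It is, because section 8.1 names no multiplier.
- **The arm A point is unproven.** The documents cannot show that arm A has fewer than 7 evaluable, and other sections keep the two-arm text too. It supports only a qualification.

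**Conclusion.** The concern holds. The stated length of 22.4 is a known-SD value. The t interval for 7 scores is 27.9 long at a sample SD of 15.1, or 26.8 in expectation if 15.1 is the true SD and scores are normal. The plan's only precision figure for its primary outcome is thus too favourable: the t length is 20 to 25% greater, depending on how the 15.1 is read.

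This should be corrected, but it does not undermine the design. Neither the sample size nor the UH3 rule depends on it. The arm A point is secondary: the figure may not describe that arm, and the documents do not settle it. The silence of section 8.1 on the method for means is a gap to close rather than an error.

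**What to change.** 1. In section 2.7.A, replace the length and the example with the t-based values and state their condition: *with 7 evaluable participants in an arm and a sample SD of 15.1, the 95% t interval (6 df) is about 27.9 points long, e.g. 66.0 to 94.0 around a mean of 80.*
2. In the same place, replace the claim that the figure applies to both arms with a note that arm A stopped enrolling (section 3.3), and give the length at arm A's actual evaluable number.
3. In section 8.1, state that confidence intervals for means use the t distribution with n − 1 df, on the transformed scale where a transformation is applied. Name the interval method to be used if the median is reported instead. This also settles the intervals for mean ethanol consumption and mean adherence.

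The cost is one corrected figure, one qualifying clause and a short addition to section 8.1. The stated precision becomes less favourable. The sample size does not need to change.

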3. INTERVENTION

3.1 INTERVENTION OVERVIEW

The study will randomize 16 HIV+ persons with past year heavy alcohol consumption (by NIAAA definition of at risk drinking) and chronic pain (defined as bodily pain of moderate to severe intensity lasting for ≥ 3 months). Existing Russia ARCH participants will be offered to be screened for this study. Recruitment beyond First St. Petersburg Pavlov State Medical University (PSMU) will occur at local NGOs, Russia ARCH network hospitals including the major clinical HIV and addiction hospitals. Some participants may be screened over the phone, but all interested potential study participants will ultimately be invited for an in-person screening of eligibility at PSMU. After eligible participants are consented and enrolled, the RA will complete screening for eligibility by conducting a rapid HIV test for non-ARCH participants, a urine drug test, and blood draw for AST/ALT testing and testing all women for pregnancy (urine). Once AST/ALT results are received, participants will be notified by phone and if eligible, will be invited to return to Pavlov for their baseline visit.

At the baseline visit, participants will be administered the naloxone challenge and observed for signs of opioid withdrawal for 20 minutes. Naloxone blocks the effects of opioids. It works only if it is injected and lasts about 30 minutes. It is used in hospitals and by emergency services to reverse the effects of a heroin or other opioid overdose. It will cause withdrawal if injected into someone who is currently physically dependent on opioids and will be administered to make sure that the participant is not physically dependent on heroin or other opioids before s/he is given oral naltrexone. The naloxone challenge will only be administered if the information the participant provides to the staff indicates that s/he is not physically dependent on heroin or other opioids and if his/her urine drug test is negative. The challenge will be done by administering 0.8-mg naloxone slowly intramuscularly. The participant will be observed by a research assessor for signs of withdrawal for 5-20 minutes. If the participant experiences withdrawal after the naloxone test, his/her symptoms may be treated with 150mcg clonidine or 2mg of benzodiazepine orally and will go away in 45-60 minutes. As withdrawal symptoms precipitated by naloxone typically resolve within 20 minutes without treatment, use of these medications will be decided on a case-by-case basis by the treating Russian physician-investigator.

In the consent form, participants will be alerted that they may experience the following side effects if they need to be treated with clonidine or benzodiazepine:

The most frequent side effects (which appear to be dose-related) of clonidine are dry mouth, drowsiness, dizziness, constipation and sedation. The most frequent side effects of phenazepam are drowsiness, sedation, muscle weakness, and ataxia. These side effects generally decrease on continued administration and are a consequence of CNS depression.

The participant will not be started on the study medication until s/he passes a naloxone challenge, which means that s/he has no signs or symptoms of opioid withdrawal after naloxone is administered.

If the participant fails the naloxone challenge, s/he will be invited to come back within a week to repeat the challenge. Participants who pass the naloxone challenge will then complete the study assessment, cold-pressor testing and be randomly assigned to either low-dose naltrexone or standard-dose nalmefene. Study medication will be provided by trained physicians, who will instruct participants in proper medication administration and adherence.

Study participants, investigators, staff, and physicians administering the medications will be unaware of specific group assignment.

Participants will be treated for 8 weeks, and outcomes (alcohol reduction, tolerability, side effects, medication adherence and discontinuation, and willingness/desire to continue to take medication at the end of the study) will be evaluated at the end of treatment.

Throughout the course of the study, participants will be expected to come in for five in-person assessments. The schedule of study in-person visits/assessments are as follows: baseline, 2, 4, 6, and 8 weeks. At weeks 4 and 8, full study visits will occur, including assessments of tolerability of medication, reduction in alcohol use, medication discontinuation, treatment side effects, self-reported pain, and experimental cold pain tolerance (cold-pressor test). Participants will also be instructed to keep a daily diary to record pain severity, alcohol use, and medication adherence. Weeks 2 and 6 will be short visits, at which a brief assessment of tolerability, side effects, and adherence will occur.

Visits will be preceded by phone/text reminders to the participant or alternate contacts.

The text message will read: "This is a reminder that your visit to Pavlov Medical University is scheduled for ____ at _____. Please reply to confirm or call [name] to reschedule."

